#### 5.4.5. Handling of Missing Data

Should missing data occur, the data will be analysed as recorded in the study eCRFs, that is, analyses will be performed on patients with non-missing values. However, the number of missing values for data elements will be reported, and the likely impact of missing data on the analysis and the pattern of the missing information will be assessed.

Depending upon the amount of missing data, and whether there is evidence of bias in the missing data (e.g., differences between patients with and without missing data), an imputation strategy, such as multiple imputation, may be performed. If an imputation strategy is undertaken, a sensitivity analysis will be carried out comparing the results from the complete case analysis (where records with missing data will be dropped) and the full set analysis including the imputed data. Full details on handling of missing data will be described in detail in the SAP.

Handling of missing item responses in QoL and sleep questionnaires will be performed according to their respective scoring manuals.

#### **5.4.6.** Limitations of Research Methods

The intention of this Phase IV study is to collect data on the impact of absorbent pants on the spontaneous resolution of NE, as well as children and parents/carers QoL and sleep quality. The primary endpoint relies on the completion of a diary by the participant's family. Failure to adhere to the clinical investigation plan and complete the diary information may result in a significant amount of missing data. Information bias will be minimised by using standard eCRF, questionnaires and physicians' training on the study clinical investigation plan. The patients' interpretation and understanding of the questionnaires and different educational backgrounds may also influence the results.

The sites selected will be a convenience sample and may not be representative of the geographic distribution or the clinic/hospital type or size in each of the participating countries. The enrolment will be competitive. At the patient level, consecutive enrolment will be employed to minimise selection bias. Potential selection bias arising from the lack of complete enrolment of potentially eligible patients will be reduced by maintaining screening logs at sites.

Several features of this study have been selected based on the experience of the members of the Scientific Committee. In order to reduce the heterogeneity of the patient population, the study will randomise patients who present with NE every night for 7 months (6 months prior to

baseline, and the 4-week run-in period). These characteristics are shared by most of the patients referred to specialist care. However, selection of patients from hospital/clinic-based specialist care may not be representative of the pool of patients with NE assessed in the community setting by paediatricians and general practitioners.

The equivalence margin of 2 dry nights per week has been determined based on the feedback of patients and families; they would not consider an effect of only 1 night a week clinically significant.

The intervention period is limited to 4 weeks; a longer period may not be acceptable for families. The likeliness of observing a spontaneous resolution of NE in this 4-week period is limited, which carries the risk of concluding to the equivalence of the 2 treatment strategies by lack of any change in either group. The duration of the study period should be kept in mind in the interpretation of the study results.

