#### 4.3.1. Inclusion Criteria

The following criteria must be met for the participant to be enrolled in the study:

- 1. Patient aged between 4–8 years at the time of enrolment
  - a. To be categorised in the younger participant group, participants must be aged 4-<6 years
  - b. To be categorised in the older participant group, participants must be aged ≥6-8 years
- 2. Have a clinical diagnosis of monosymptomatic primary NE
- 3. Have been dry in the day for  $\geq 6$  months prior to enrolment
- 4. Have on average no more than 1 dry night per month during the past 6 months at enrolment
- 5. Using absorbent pants/nappies to manage NE for at least 6 months prior to enrolment
- 6. Have an informed consent form (ICF) signed by their parent(s)/carer(s)
- 7. For randomisation: have NE 7 nights per week over Week 4/last week of the run-in period

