#### 4.3.4. Screen Failures

Screen failures are defined as patients who were consented to participate in the study but are not subsequently randomly assigned to study treatment, for any reason identified before, during, or at the end of the run-in period.

A minimal set of screen failure information is required to ensure transparent reporting of screen failure subjects to meet the Consolidated Standards of Reporting Trials (CONSORT) publishing requirements and to respond to queries from regulatory authorities. Minimal information

includes demographics, screen failure details, eligibility criteria, and any serious adverse event (SAE).

These patients should have the reason for study withdrawal recorded as 'Screen failure'; this reason for study withdrawal is only valid for patients who were not randomised.

Individuals who do not meet the criteria for randomisation in this study may be re-screened one time, after an additional run-in of 1 week.

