#### 4.7.3. Visit 2 - End of Run-in/Randomisation Visit

The following assessments will be performed for all patients at end of run-in/randomisation visit (Day  $28 \pm 7$ ):

- Any AEs occurred since the baseline visit
- Concomitant medications for AEs
- Review of diary data
- DryNites® Clinical Trial Questionnaire (all participants)
- Patient and parents/carers QoL and sleep questionnaires: PinQ, WHOQOL, PDSS,
   CIS (for randomised participants only)

The Investigator will confirm NE frequency by assessing the data recorded in the diary by the participants/parents/carer at the randomisation visit (Day  $28 \pm 7$ ). Only participants who experience NE at a frequency of 7 nights per week during the last week of the run-in period (no dry night) will be randomised.

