8.2 Adjustments for Covariates and Factors to be Included in Analyses

The baseline of any applicable Patient Reported Outcomes (PRO) will be used as covariate in the analysis of covariance (ANCOVA) planned on secondary endpoints analysis.

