15.1.2 Missing Data Methods for Primary Analysis Variable

Multiple imputation technique will be used to address missing values for primary endpoint in case of percentage of missing data will be $\geq 20\%$. Multiple imputation it's superior to single imputation in reducing statistical bias by building in random error into the imputation. This prevents underestimation of the degree of variability in the data, which affects the estimate of the standard error.

Document:	Y:\Kimberly-Clark\DryNites\Documentation\SAP\DryNites_SAP_v1.0_20200203		
Author:	[name]	Version Number:	1.0
		Version Date:	03Feb2020
Template No.:	RWI_TP_BIOS0013 Revision 1	I	Reference: RWI_WI_BIOS0015
Effective Date:	15Jun2018		

The following steps will be used:

- Differences on all key and outcome variables between patients with missing versus nonmissing values will be described and tabulated.
- Missing data will be imputed using SAS PROC MI under the assumption that the missing values are missing at random (MAR). This assumption requires that missing values be related to measured covariates, with no unmeasured related covariates.
- Results will be aggregated across the multiply imputed data sets using SAS PROC MIANALYZE.

The multiple imputation model will include the primary outcome as the number of wet nights during the last week on the 4 weeks period after randomisation, randomisation group, average number of wet nights during the run-in period, age and sex. The number of imputation data sets to be created is 100.

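### Section 5.4.6 describes a more uniform population than the eligibility rules select, and the primary comparison leaves out the run-in diary that would show the difference

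*Protocol*

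**What the plan says.** Protocol 5.4.6 (Limitations) presents the population as a way of reducing heterogeneity: "the study will randomise patients who present with NE every night for 7 months". It makes up the seven months from the six before baseline plus the run-in.

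The operative rules are these:

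- Criterion 4 (Protocol 4.3.1): "Have on average no more than 1 dry night per month during the past 6 months at enrolment".
- Criterion 7 (Protocol 4.3.1), for randomisation: "have NE 7 nights per week over Week 4/last week of the run-in period". Protocol 4.7.3 repeats the same one-week check against the diary: "Only participants who experience NE at a frequency of 7 nights per week during the last week of the run-in period" proceed.
- Children who miss the randomisation criterion "may be re-screened one time, after an additional run-in of 1 week" (Protocol 4.3.4).

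The diary runs daily from the morning after baseline (Protocol 4.7.2), so the earlier run-in weeks are recorded.

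On analysis, SAP 15.1.3 takes the primary difference and 95% interval from PROC TTEST for independent groups. SAP 8.2 provides covariates only for the secondary questionnaires: "The baseline of any applicable Patient Reported Outcomes (PRO) will be used as covariate". Run-in wetness has a modelling role only in SAP 15.1.2, where the imputation model includes "average number of wet nights during the run-in period, age and sex". That model is run only if at least 20% of primary data are missing. Randomisation is stratified by age group alone (Protocol 4.3.5).

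**The concern.** No rule limits dry nights in run-in Weeks 1–3, and criterion 4 expressly permits some before enrolment. A child re-screened because of a dry night in Week 4 has, by definition, had a dry night in the run-in. The statement in 5.4.6 therefore cannot be true of everyone the rules admit. It matters because Protocol 1.2 justifies the choice of population by its uniformity, so a reader of the results would take the sample to be stricter than it is.

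The analysis side follows from this. Every randomised child scores 7 of 7 in the qualifying week, so that week cannot tell children apart. The rest of the run-in diary can, to the extent that children differ. The SAP treats run-in wetness as predictive when it imputes the outcome but leaves it out when it estimates the effect. What is at stake is the accuracy of the population description and some width in the interval that decides equivalence.

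**Working it through.** **1. The plan's own figure.** Inputs from Protocol 5.2: 15 continuing and 30 discontinuing children, 7 nights each, wet-night probabilities 0.95 and 0.80, margin 2/7, 95% interval.

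SE = √(0.95×0.05/(7×15) + 0.80×0.20/(7×30)) = √(0.000452 + 0.000762) = 0.0348.

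Power ≈ Φ((0.2857 − 0.15)/0.0348 − 1.96) = Φ(1.93) ≈ 97.3%.

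Simulation by the plan's method gives 97.8%, within two points of the stated 99%. Analysing the same simulated children with a t interval gives about 91% power if variances are pooled and about 97% with Welch. SAP 15.1.3 does not say which PROC TTEST interval is meant. This bears on the fix below.

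**2. What the rules allow, side by side.**

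| Period | Section 5.4.6 | Entry rules |
|---|---|---|
| 6 months before baseline | wet every night | average of up to 1 dry night a month, so about 6 |
| Run-in Weeks 1–3 | wet every night | no limit |
| Run-in Week 4 | wet every night | 7 of 7, or 7 of 7 in one further week |

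**3. A child exactly at the criterion 4 limit.** Assume nightly wet probability 29/30 and independent nights.

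- Passes the one-week test: (29/30)^7 = 0.79. With the retry: 1 − (1 − 0.79)² = 0.96.
- At least one dry night in the 21 nights of Weeks 1–3: 1 − (29/30)^21 = 0.51. At least three: 0.03.

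A dry night or two in the run-in is thus quite compatible with entry. Several are possible but uncommon.

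**4. What adjustment would gain.** The documents give no between-child variation, so this is an assumption shown as a range. Each child's wet probability is drawn from a beta distribution with mean 0.95 and intraclass correlation 0.05–0.3. Criterion 4 is represented as a cap on dry nights in 180 earlier nights. Children must then pass 7 of 7 at the first or second attempt. Let r be the correlation, among those who pass, between average run-in wet nights and the count in a later week with no treatment effect. Adjustment removes r² of the outcome variance and multiplies the interval width by √(1 − r²). Squares were taken before rounding.

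| How criterion 4 works | r | Variance removed | Interval narrower by |
|---|---|---|---|
| Accurate (at most 6 of 180 dry) | 0.12–0.20 | 1.5–4% | 1–2% |
| Recall admits twice the limit (12 of 180) | 0.18–0.29 | 3–9% | 2–4% |
| Does not select at all | 0.33–0.59 | 11–34% | 6–19% |

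In the same model, 7–28% of randomised children have at least one dry night in Weeks 1–3 when criterion 4 is accurate, and 17–48% when it does not select.

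**The case against.** The strongest reply is that this is a loose sentence in a limitations section. The operative criteria agree with one another, Protocol 1.2 says more carefully that these children usually wet every night, and nobody is enrolled from 5.4.6. The unadjusted interval is valid under randomisation and already allows for chance imbalance, so covariate adjustment is an efficiency choice. Nor is the run-in diary wholly unused: SAP 15 summarises diary data descriptively with change from baseline, and run-in wetness enters the imputation model. All of this stands. It limits the size of the point but does not remove the contradiction, and a prognostic baseline value is still left out of the main estimate.

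A reader might infer that the trial will fill with children who already have many dry nights. The documents do not support that. At a common wet probability of 0.95, 1 − 0.95^21 = 66% would have at least one dry night in Weeks 1–3. But that figure assumes all children are alike, in which case adjustment gains nothing. It also borrows the plan's assumed end-of-trial rate for the continuing arm. Likewise, the one-week test with a retry would pass 38% of children wet on 80% of nights (0.80^7 = 0.21; 1 − 0.79² = 0.38) and 73% of those wet on 90%. Those children have about six and three dry nights a month, and criterion 4 should exclude them. The baseline questionnaire (Protocol Table 3) also excludes children wet on 1–6 nights a week.

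**Conclusion.** The point holds at modest size. Section 5.4.6 contradicts criteria 4 and 7, the Visit 2 check and the re-screen rule, and the passages must be reconciled. The primary comparison omits a baseline measure that the SAP itself treats as predictive.

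A reader might go further and conclude that the equivalence result is biased. It is not: allocation is random, so run-in wetness is balanced in expectation. A reader might also take the 6–19% gain as the likely one. It arises only if criterion 4 selects nobody. With the criterion working, expect about 1–2%, or 2–4% if recall is twice as lenient as intended. These ranges rest on the assumed beta-binomial model, independent nights given the child, and no treatment effect. The documents do not show how many children with run-in dry nights will enter.

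**What to change.** 1. **Primary model (SAP 8.2 and 15.1.3).** Obtain the difference and 95% interval from a linear model with arm, average run-in wet nights per week and, in the overall analysis only, age group as the randomisation stratum. Average over all recorded run-in nights, including any re-screen week, because Visit 2 falls at Day 28 ± 7 and run-in length varies. Let residual variances differ by arm, or use robust standard errors. A common-variance model could lose more than the covariate gains: on the plan's assumptions at 15 and 30, pooling gives about 91% power against about 97% without it.
2. **Population (Protocol 5.4.6).** Reconcile it with 4.3.1, 4.3.4 and 4.7.3, so that while those criteria stand it describes the children they select.
3. **Reporting.** Tabulate run-in dry nights and re-screen status by arm.

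Cost: SAP wording, one or two degrees of freedom, and deriving the run-in average in every case rather than only when imputation is triggered. The diary data are already collected, and recruitment is unaffected.

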#### **6 STUDY MANAGEMENT**

This study will be performed by IQVIA with guidance, input, review, and approval of Kimberly-Clark, including development of materials, recruitment, training and management of sites, EDC and data management and analysis.

#### 6.1. Data Entry/Electronic Data Capture

All data will be collected and entered directly into the EDC system. The EDC system is designed to meet the 21 CFR part 11 regulations for EDC. All participating sites will have access to the data entered regarding the individual site its own enrolled patients. All sites will be fully trained on using the on-line data capture system, including eCRF completion guidelines and help files. Sites will be responsible for entering extracted patient data into a secure internet-based EDC registry database via the eCRF. Investigators and site personnel will be able to access their account with a username and password. All eCRFs should be completed by designated, trained personnel or the study coordinator, as appropriate. In most cases, the eCRF should be reviewed, electronically signed, and dated by the Principal Investigator. All changes or corrections to eCRFs are documented in an audit trail and an adequate explanation is required.

For electronic patient-reported outcomes (ePROs), the data entered by the participants/parents/carers will be directly captured into the EDC. The parents will be provided

a link to the EDC at baseline. They will access their ePRO account with a username and password and complete the questionnaires using a site-based electronic device (such as smartphones, iPad or tablet), laptop or desk computer, or parent's own device, if completed off-site.

Similarly, the diary will be directly captured in the EDC, using the patient's own device at home.

#### 6.2. Source Documents

In most cases, the source documents are contained in the patient's medical record and data collected on the CRFs must match the data in the medical records. In some cases, the CRF, or part of the CRF, may also serve as source documents. In these cases, a document should be available at the Investigator's site and clearly identifying those data that will be recorded in the CRF, and for which the CRF will stand as the source document. All original source documentation is expected to be stored at the site for the longest possible time required by local applicable regulations.

#### 6.3. File Retention and Archiving

To enable evaluations and/or audits from regulatory authorities or the Sponsor, the Investigator agrees to keep records, including the identity of all participating patients, all original signed informed consent forms, copies of all CRFs, SAE forms, source documents and adequate documentation of relevant correspondence (e.g., letters, meeting minutes, telephone calls reports). The records should be retained by the Investigator according to local regulations, or as specified in the study contract, whichever is longer.

Each site will receive a study site file at study initiation which contains all documents necessary for the conduct of the registry and is updated throughout the study. This file must be available for review in the event the site is selected for monitoring, audits, or inspections and must be safely archived for at least 5 years after the release of the final study report. Documents to be archived include the patient enrolment log and the signed ICF. In the event that archiving of the file is no longer possible at the site, the site will be instructed to notify the Sponsor.

#### 6.4. Quality Assurance and Monitoring

A study monitoring plan, including for-cause monitoring, that is appropriate for the study design will be developed and implemented.

During the remote site initiation visit, the monitor will provide training on the conduct of the study to the Investigator, co-Investigator(s), and all site staff involved in the study. In order to ensure the integrity of the data, sites will be monitored. Remote and on-site monitoring will be performed by IQVIA monitors to examine compliance with the clinical investigation plan and adherence to the data collection procedures, to assess the accuracy and completeness of submitted clinical data, and to verify that records and documents are being properly maintained for the duration of the study. The monitor will perform source data verification by review of original patient records.

The monitor will close out each site remotely after the last patient's final follow-up assessment is completed, all data have been entered and all outstanding monitoring issues have been resolved or addressed. All monitoring procedures and frequency of monitoring visits will be described in a monitoring plan. Monitor contact details for each participating site will be maintained in the Investigator Site File.

Representatives of the Sponsor's quality assurance unit/monitoring team and competent regulatory authorities must be permitted to inspect all study-related documents and other materials at the site, including the Investigator Site File, the completed eCRFs and the patients' original medical records. Audits may be conducted at any time during or after the study to ensure the validity and integrity of the study data.

#### 6.5. Data Management

A data management plan will be created before data collection begins and will describe all functions, processes, and specifications for data collection, cleaning, and validation. The eCRFs will include programmable edits to obtain immediate feedback if data are missing, out of range, illogical or potentially erroneous. Concurrent manual data review will be performed based on parameters dictated by the plan. Ad hoc queries will be generated within the EDC system and followed up for resolution.

High data quality standards will be maintained, and processes and procedures utilised to repeatedly ensure that the data are as clean and accurate as possible when presented for analysis.

Data quality will be enhanced through a series of programmed data quality checks that automatically detect out of range or anomalous data.

#### 6.6. Study Governance

A Scientific Committee comprised of 4 members will oversee the conduct of the study. The Scientific Committee is responsible for the following: determination of study objectives and design, review and approval of the study clinical investigation plan, review and approval of the clinical study report, interpretation of the study results and any recommendations based on the clinical study results. The list of members is presented in the Contacts section.

#### 7 SAFETY REPORTING

All AEs, regardless of relationship to the study treatment or intervention, will be monitored and reported throughout the entire course of the study. The AE reporting period begins when the patient is consented to participation in the study (date of first signature of informed consent) and continues through the study discontinuation date. AEs will be recorded on the appropriate eCRF forms.

#### 7.1. **Definitions**

#### 7.1.1. Adverse events (AEs)

An AE is the development of any untoward medical occurrence in a patient or clinical study subject administered a medicinal product and which does not necessarily have to have a causal relationship with the product. An AE can therefore be any unfavourable and unintended sign (including an abnormal laboratory finding, for example), symptom, or disease temporally associated with the use of a product, whether or not considered related to the medicinal product. The term AE is used to include both serious and non-serious AEs.

Pre-existing conditions that worsen during a study are to be reported as AEs. If, according to the Investigator, there is a worsening of a medical condition that was present prior to the administration of the intervention, this should also be considered a new AE and reported. Any medical condition present prior to the administration of the intervention that remains unchanged or improved should not be recorded as an AE at subsequent visits.

